9.2 Subject Enrollment

After being informed of the nature of the study, the subject will provide written informed consent that has been approved by the sponsor and the appropriate IRB of the respective clinical site. A minimum of one hundred and twenty-five (125) subjects will be enrolled in the study at a minimum of 4 US sites with competitive enrollment not to exceed 40 subjects per site.

A subject is considered enrolled in the study when:

- it is confirmed that the ICF is signed,
- they meet all pre-operative inclusion criteria,
- they meet no pre- or intra-operative exclusion criteria,
- they have received Parietene™ DS Composite Mesh intraoperatively.

Adverse events will be collected starting at the time of skin incision and the subject must be followed for the full 24 months if the procedure was begun or completed with the study device. If ICF signature occurs more than 30 days before the procedure the subject is to be reconsented. No study procedures will be performed until informed consent form has been completed.

The elective ventral hernia repair procedure will be performed per the intraperitoneal onlay mesh technique (IPOM) by open or laparoscopic approach.

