10.12.3 Study Exit

A study exit eCRF is required for all subjects. Prior to exiting a subject from the study, it is recommended to follow the subject until all ongoing system and/or procedure related AEs are resolved or unresolved with no further actions planned. All data available through the time of the subject's exit will be used for analysis.

MDT17051PDS Version 4.0 Page 31 of 56

Subjects are urged to remain in the study as long as possible but may be exited from the study for any of the following situations:

- Study completed
- Subject lost to follow-up
- Subject death
- Subject did not meet inclusion/exclusion criteria
- Subject was not implanted with a (investigational) device
- Subject did not provide consent <or data use protection authorization>
- Subject chooses to withdraw (e.g., consent withdrawal, relocation to another geographic location)
- Investigator deems withdrawal necessary (e.g., medically justified, inclusion/exclusion criteria not met, failure of subject to maintain adequate study compliance)

If discontinuation is because of safety or lack of effectiveness, the subject may be asked to be followed for collecting safety data outside the clinical investigation.

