14.1 Statistical Test Methods & Analysis Populations

Statistical analysis consists mainly of a descriptive analysis, and will be performed on:

- the Full Analysis Set (FAS, including any subject enrolled and receiving study device) representing the primary analysis population,
- the Per Protocol Analysis Set [PPAS, a subset of the FAS of subjects who meet the primary endpoint (12-month assessment) and who did not deviate (major) from the protocol], as confirmatory analysis and,
- the Safety Analysis Set (any subject with skin incision including those who are 'screen failure during surgery') for safety and efficacy analysis

Continuous variables will be summarized using counts, means, standard deviations, medians, minimum and maximum. Categorical variables will be summarized using frequencies and percentages.

Time to events analyses using Kaplan Meier estimates and curve will be performed for time to recurrence or to adverse event occurrence

Changes to the planned statistical analysis as defined in the protocol will be documented in the statistical analysis plan and clinical study report.

Statistical analysis will be performed using SAS version 9.4 and Minitab® Version 15.0.

MDT17051PDS Version 4.0 Page 41 of 56

For the purposes of study analysis and statistics adverse event will be defined as procedure related adverse events and adverse device effects.

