CCS	Carolina Comfort Scale: it is a validated, disease-specific, quality of life (QOL) questionnaire developed for patients undergoing hernia repair.					
CE Mark	European Community Marking that indicates that the product (device) complies with the European Legislation and so can go to EU market.					
CI	Confidence Interval					
CIP	Clinical Investigation Plan (can be used synonymously with Protocol)					
Device Deficiency	Inadequacy of a medical device with respect to its identity, quality, durability, reliability, safety or performance. Note: Device deficiencies include malfunctions, use errors, and inadequate labeling.					
FAS	Full Analysis Set – An analysis set including any subjects enrolled and receiving study device					
Hernia recurrence	A clinically manifested bulge or a protrusion exacerbated by a Valsalva maneuver.					
IA	Interim Analysis					
IRB	Institutional Review Board					
ISO	International Organization for Standardization					

Version [Final v3.0]

Page 5 of 18

Term/Abbreviation	Definition
PMCF	Post market clinical follow up
PPAS	Per Protocol Analysis Set – An analysis set consisting of a subset of the full analysis set of subjects who meet the primary endpoint (12-month assessment) and who did not deviate (major) from the protocol
QOL	Quality of Life
SAE	 Serious Adverse Event - Adverse event that: a. Led to a death, b. Led to a serious deterioration in the health of the subject, that either resulted in: Resulted in a life-threatening illness or injury, or Resulted in a permanent impairment of a body structure or a body function, or In-patient or prolonged hospitalization, or Medical or surgical intervention to prevent life threatening illness or injury or permanent impairment to a body structure or a body function, or Led to fetal distress, fetal death or a congenital abnormality or birth defect. Note: Planned hospitalization for a pre-existing condition, or a procedure required by the CIP, without serious deterioration in health, is not considered a serious adverse event.
SADE	Serious Adverse Device Effect - Adverse device effect that has resulted in any of the consequences characteristic of a serious adverse event.
SAP	Statistical Analysis Plan
SAS	Safety Analysis Set is an analysis set including any subject pre-operatively eligible for the study and with skin incision, including those who are 'screen failure during surgery.
USA	United States of America

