7.1.3. Analysis Sets

Statistical analysis will be performed on:

- Full Analysis Set (FAS): including any subject enrolled and receiving study device, representing the primary analysis population, for Efficacy and Safety analyses
- Per Protocol Analysis Set (PPAS): a subset of the FAS of subjects who meet the primary endpoint (12month assessment) and who did not deviate (major) from the protocol, as confirmatory analysis for Efficacy and Safety analyses,
- Safety Analysis Set (SAS): any subject pre-operatively eligible with skin incision including those who are 'screen failure during surgery', used for Safety analysis.

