7.12. Changes to Planned Analysis

Some minor changes were made in this SAP in regard to the statistical methodology as described in CIP v1.0 document. These changes are related to Analysis Sets definitions and the use of these analysis sets for endpoints assessment.

From CIP v1.0, analysis sets were defined as follows:

- the Full Analysis Set (FAS, including any subject enrolled and receiving study device) representing the primary analysis population,
- the Per Protocol Analysis Set [PPAS, a subset of the FAS of subjects who meet the primary endpoint (12month assessment) and who did not deviate (major) from the protocol], as confirmatory analysis and,
- the Safety Analysis Set (any subject with skin incision including those who are 'screen failure during surgery') for safety and efficacy analysis

From SAP v1.0, analysis sets are defined as follows:

- Full Analysis Set (FAS): including any subject enrolled and receiving study device, representing the primary analysis population, for Efficacy and Safety analyses.
- Per Protocol Analysis Set (PPAS): a subset of the FAS of subjects who meet the primary endpoint (12month assessment) and who did not deviate (major) from the protocol, as confirmatory analysis for Efficacy and Safety analyses,
- Safety Analysis Set (SAS): any subject pre-operatively eligible with skin incision including those who are 'screen failure during surgery', used for Safety analysis.

Any major change in planned analysis as described in this SAP would result in SAP amendment.

Validation level I will be applied for endpoints evaluated at the first interim analysis.

First interim analysis (Safety analysis at 3-months) will evaluate subject's disposition, screening data, demographics characteristics and occurrence of procedure or device-related AE occurring within 3-month from surgery (see IA#1 parameters in section 7.8.1.).

Validation level III will be applied for any endpoint evaluated during second interim analysis or final analysis.

Validation levels are defined as follows:

- Level I: The peer reviewer independently programs output and then compares the output with that generated by the original Statistical Programmer.
- Level II: The peer reviewer reviews the code; where appropriate, performs manual calculations or simple programming checks to verify the output.
- Level III: Original Statistical Programmer performs a visual inspection of the code and output to confirm functionality.

9. References

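### As worded, the SAP's Safety Analysis Set omits a subject who received the mesh and is later found to have failed a pre-operative criterion, and no other analysis set includes that subject

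*SAP*

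**What the plan says.** **Safety set, protocol.** Section 14.1 has "the Safety Analysis Set (any subject with skin incision including those who are 'screen failure during surgery') for safety and efficacy analysis". Skin incision is the only condition.

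**Safety set, SAP.** Section 7.1.3 has "any subject pre-operatively eligible with skin incision including those who are 'screen failure during surgery', used for Safety analysis". The added condition sits in the opening words, "any subject pre-operatively eligible with skin incision". The abbreviation list in SAP section 2 carries the same restriction: "Safety Analysis Set is an analysis set including any subject pre-operatively eligible for the study and with skin incision".

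**Disclosure.** SAP 7.12 opens with "Some minor changes were made in this SAP in regard to the statistical methodology" and prints the two sets of definitions one after the other. It gives no reason for the eligibility condition. The comparison is with CIP v1.0, but the current protocol (v4.0) still has the unrestricted wording.

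**Enrolment.** Protocol 9.2 makes enrolment depend on signed consent, on receipt of the mesh, on the condition that "they meet all pre-operative inclusion criteria", and on no pre-operative or intra-operative exclusion applying. Section 10.12.1 repeats this.

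**The other two sets.** In both documents the FAS requires enrolment plus receipt of the device, and the PPAS is a subset of the FAS.

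**Exit.** Protocol 10.12.3 lists "Subject did not meet inclusion/exclusion criteria" among the exit reasons and gives unmet criteria again as an example of withdrawal by the investigator. It also says that whatever was collected before exit is to enter the analysis, without naming a set.

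**The concern.** A safety set normally holds everyone exposed to the procedure or device. Eligibility breaches that come to light later are usually dealt with by removing the subject from the per-protocol set only. Here three definitions combine to give a different result. Consider a subject who received the mesh and whose BMI is found at source verification to have been above 45, or who turns out to have taken part in another investigational study within the 30-day limit. On the literal wording this subject has no analysis set.

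Other planned outputs do not make up for that. SAP 7.10 bases both the adverse event proportions and the listings on FAS, PPAS and SAS. SAP 7.1.2 reports deviations on FAS subjects. SAP 7.1.1 tabulates discontinuation reasons on FAS and SAS. The subject's events, eligibility breach and exit reason could all go unreported in the tables. Yet protocol 9.2 requires 24 months of follow-up once the procedure was begun or completed with the study device, so the data could well exist.

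**Working it through.** **1. Membership.** No plan figure tests this claim, so the check is to apply the definitions to every kind of implanted subject. The rules are:

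- Enrolled = consent + mesh received + pre-operative criteria passed + intra-operative criteria passed (protocol 9.2, 10.12.1).
- FAS = enrolled + device received; PPAS is contained in FAS (SAP 7.1.3).
- SAS, protocol = skin incision (14.1).
- SAS, SAP = skin incision + pre-operatively eligible (7.1.3).

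| Pre-operative criteria | Intra-operative criteria | FAS | PPAS possible | SAS (protocol) | SAS (SAP) |
|---|---|---|---|---|---|
| passed | passed | yes | yes | yes | yes |
| passed | failed | no | no | yes | yes |
| failed | passed | no | no | yes | **no** |
| failed | failed | no | no | yes | **no** |

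The two rows with a failed pre-operative criterion are in no SAP set. The protocol's SAS wording keeps all four rows.

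**2. Do the screen-failure categories catch the case?** Protocol 10.12.2.1 covers a pre-operative failure found before the procedure. Section 10.12.2.2 covers an intra-operative failure found during it. A pre-operative failure found after implantation fits neither. The exit reasons in 10.12.3 are compatible with such a case, although the general one may also be meant for screen failures.

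**3. Size.** The documents give no count of such subjects, so what follows is illustration. The denominator is the planned enrolment, which reproduces: 100 / (1 − 0.20) = 125.

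*Common events.* Take an 11% rate, the low end of the planning range in protocol 14.2. Of 125 enrolled, 0.11 × 125 = 13.75, say 14, have an event: 14/125 = 11.2%. Add one omitted subject with an event: 15/126 = 11.9%. The shift is 0.7 points. The 95% half-width at 11% and N = 125 is 1.96 × √(0.11 × 0.89 / 125) = 5.5 points.

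*Rare serious device effects.* One such event in one omitted subject: 0/125 = 0% is reported, against 1/126 = 0.8%. At the first interim, with one such subject beside the 30 enrolled: 0/30 = 0% against 1/31 = 3.2%.

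*Chance that at least one subject with an event is left out.* Assume k such subjects and an event rate r of 11% to 25%. The formula is 1 − (1 − r)^k.

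| k (assumed) | r = 11% | r = 25% |
|---|---|---|
| 1 | 11% | 25% |
| 3 | 1 − 0.89³ = 29% | 1 − 0.75³ = 58% |
| 5 | 1 − 0.89⁵ = 44% | 1 − 0.75⁵ = 76% |

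The 11% to 25% range comes from studies of other meshes. It is not a rate for ineligible subjects.

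**The case against.** The strongest reply is that eligibility in these documents is a decision taken at a point in time. Protocol 10.2 uses the screening visit to confirm it, the first note to the schedule of events has it reconfirmed on the day of surgery, and 10.12.2.1 speaks of a determination made before the procedure. On that reading the SAP's phrase merely separates pre-surgery screen failures (out) from failures during surgery (in). A subject passed as eligible and then incised stays in the SAS and probably in the FAS. No passage reverses enrolment after implantation. The 10.12.3 sentence on using data up to exit points the same way. SAP 7.1.1 and 7.1.2 could then handle the breach as an exit reason and a major deviation.

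This reading is plausible and may be what the authors meant. But neither document states it, and the 10.12.3 sentence assigns the subject to no set while the SAP confines safety output to three sets. In an unblinded single-arm study, membership should not be left to interpretation once outcomes are known.

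Other parts of the reply stand in full:

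- A reader might infer that any subject later found ineligible drops out everywhere. That is wrong for the intra-operative exclusions, such as CDC wound class 2-4 or overlaid meshes, because those subjects remain in the SAS.
- A reader might infer that the change was concealed. It was not: SAP 7.12 shows both wordings, and protocol 14.1 allows analysis changes to be documented in the SAP.
- A reader might infer that the events would go unseen. Protocol 12.6 still has all adverse events recorded, and under 13.1 the independent medical monitor reviews all serious ones. The gap is in tabulated rates and listings.

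**Conclusion.** The point holds for one group: subjects who received the mesh and are found afterwards to have failed a pre-operative criterion. On the literal wording they are in no SAP analysis set, whereas the current protocol's SAS would include them. The conclusion rests on reading enrolled and pre-operatively eligible as statements of fact that can be revised later. If both mean as judged at surgery, the gap closes, but that has to be written down.

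The size is unknown because the number of such subjects is unknown. For common events the effect is probably small: in the illustration, one omitted subject with an event moves the rate by 0.7 points against a half-width of 5.5. For a serious device effect, one omission is enough to turn a non-zero rate into a reported zero.

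It is tempting to go further and say that these subjects carry higher risk, or that complications prompt the eligibility re-check, so that the omission biases safety results in the device's favour. Nothing in the documents supports either step, and the point does not need them.

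**What to change.** Three changes, all in the SAP:

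1. In section 2, 7.1.3 and 7.12, delete the pre-operative eligibility condition. The SAS is then every subject with skin incision, whenever ineligibility is found, as in protocol 14.1.
2. In 7.1.3, state that FAS membership uses eligibility as judged at the time of surgery.
3. In 7.1.2 and 7.1.3, state that a pre-operative eligibility breach found after implantation is a major deviation and removes the subject from the PPAS only.

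The cost is wording, with no new data and no additional patients. The downside is that a few ineligible subjects stay in the safety and full sets, and so also count in the FAS analysis of recurrence. The PPAS analysis shows the result without them.

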7.2. General Methodology

Statistical analysis is descriptive; some subgroup comparative analyses may be run in addition to primary and secondary endpoints, to assess impact of demographic characteristics, risk-factors, hernia characteristics and/or surgical technique applied (including mesh characteristics).

Continuous variables will be summarized using counts, means, and standard deviations, medians, minimum, maximum and 95% confidence Interval (CI). Categorical variables will be summarized using frequencies, percentages and 95% confidence interval (CI).

Statistical analysis will be implemented on overall subjects, using several analysis sets, as described previously (Section 7.1.3).

Several comparative analyses will be performed by hernia type (primary hernia versus incisional hernia) on overall subjects and on a subgroup of subjects with robotically assisted laparoscopic repair. Results of subjects operated with robotically assisted laparoscopic repair will also be compared with subjects operated with a traditional laparoscopic procedure. The following statistical tests will be used:

- Pearson Chi-square test or Exact test will be used (as appropriate) for categorical data
- Student t-test or Wilcoxon rank sum test will be used if assumptions or t-test are not verified for continuous data.

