10.7 Randomization and Treatment Assignment

No randomization will occur throughout the course of this study.

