7.3. Center Pooling

The study will be conducted in a minimum of 4 investigational sites. Screening and surgical data will be summarized for overall subjects and for each site separately, to confirm homogeneity of subject's characteristics between sites.

PPDS Statistical Analysis Plan	
Version [Final v3.0] Page 12 of 18	Medtronic

Primary and secondary endpoint analysis will be run on overall subjects. In case of imbalance regarding subject's characteristics between sites, additional subgroup analyses for primary and secondary endpoints could be performed according to investigational sites.

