7.5. Adjustments for Multiple Comparisons

Statistical analysis of primary and secondary endpoints is descriptive. No adjustment will be done.

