7.7. Treatment Characteristics

For efficacy and safety endpoints assessment, some subgroup analyses may be run according to hernia characteristics, surgical technique and mesh characteristic (number of treated hernias, mesh size, number of implanted meshes...); all these characteristics may impact efficacy and safety results.

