7.9. Evaluation of Objectives

Study objectives will be assessed through study endpoints measurement.

The primary endpoint is incidence of hernia recurrence within 12 months following Parietene[™] DS Composite Mesh use in ventral hernia repair.

Incidence of hernia recurrence within 12 months will be measured on the FAS subjects and using the following calculation formula:

[Subjects with Recurrence diagnosed within the first 12month following surgery]

[Subjects with Recurrence diagnosed within the first 12month following surgery + Subjects free of recurrence with a follow-up ≥12months]

A confirmatory analysis of primary endpoint will be run using Per Protocol Analysis Set.

Secondary endpoints

- Incidence of adverse device effects (ADEs) intra-operatively, at discharge, within 1 month, 3 months, 12 months, and 24 months following Parietene[™] DS Composite mesh use in ventral hernia repair will be primarily assessed based on FAS, and secondarily using PPAS and SAS.
- Incidence of hernia recurrence at 1, 3 and 24 months. The evaluation of hernia recurrence will be performed during a physical examination, using the formula described previously, according to the different time-points, and based on FAS and PPAS.
- Time to hernia recurrence and time to adverse device effect occurrence (from surgery time-point), will be assessed using Kaplan Meyer estimates. FAS and PPAS will be used for time to hernia recurrence, while FAS, PPAS and SAS will be used for time to ADE occurrence analysis. Time to Device-related AEs occurrence may also be assessed using Kaplan Meyer estimates.
- Carolinas Comfort Scale[™] QOL questionnaires completed pre-operatively and at 1, 12 and 24 months postoperatively will be analyzed using the Carolina Comfort Scale User Guide recommendations and programming code (see Appendix B), and based on FAS and on PPAS.

Several Subgroup analyses will be performed. Comparative analyses will be performed by hernia type (primary hernia versus incisional hernia) on overall subjects and on a subgroup of subjects with robotically assisted laparoscopic repair. Results of subjects operated with robotically assisted laparoscopic repair will also be compared with subjects operated with a traditional Laparoscopic procedure.

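### The planned robotic versus laparoscopic comparison is non-randomised but uses only unadjusted two-group tests, and the SAP does not call it exploratory

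*SAP*

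**What the plan says.** SAP 7.2 first describes the analysis as descriptive with optional subgroup work, then commits to three comparisons: primary versus incisional hernia in all subjects, the same within the robotic subgroup, and robotic versus conventional laparoscopic repair. Of the last it says: "Results of subjects operated with robotically assisted laparoscopic repair will also be compared with subjects operated with a traditional laparoscopic procedure". SAP 7.9 repeats all three straight after the endpoints, under the statement "Several Subgroup analyses will be performed".

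The tests named in 7.2 are "Pearson Chi-square test or Exact test will be used (as appropriate) for categorical data" and "Student t-test or Wilcoxon rank sum test will be used if assumptions or t-test are not verified for continuous data". No covariate, stratum, matching or site term is given for these comparisons.

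Protocol 10.7 states "No randomization will occur throughout the course of this study". Protocol 10.4 leaves the operation to each institution's standard practice. SAP 7.7, after listing hernia, technique and mesh features, notes that "all these characteristics may impact efficacy and safety results". Imbalance between sites leads only to an option in SAP 7.3: "additional subgroup analyses for primary and secondary endpoints could be performed according to investigational sites".

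On multiplicity, SAP 7.5 says "Statistical analysis of primary and secondary endpoints is descriptive. No adjustment will be done". Neither document sets a significance level for the subgroup tests, calls them exploratory or limits how their p-values may be read.

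**The concern.** Because technique is not allocated by the study, subjects repaired robotically may differ from those repaired by conventional laparoscopy in hernia type, defect size, BMI, recurrence history or site. With up to 40 of 125 subjects at one site (Protocol 9.1), technique could also cluster by site. An unadjusted test then measures a crude association that mixes technique with case mix. The SAP names likely sources of that mixing in 7.7 but specifies tests that ignore them.

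What is at stake is interpretation. SAP section 3 says the study serves to confirm safety and performance and to support EU regulatory and post-market requirements. In that setting, a small p-value for robotic repair could be taken as a property of the technique.

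**Working it through.** **The plan's own figures.** Evaluable N is 100 and attrition 20% (SAP 6): 100 / (1 − 0.20) = 125, as stated. The half-width at 3.5% is 1.96 × √(0.035 × 0.965 / 100) = 3.6 points, and at 5.2% it is 4.4 points, both as stated. Expected recurrences in 100 subjects are 3.5 to 5.2, or about 4 to 5. No group size, effect size or power is given for the technique contrast. Everything below on group size, imbalance and subgroup rates is therefore assumed.

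**CCS, no true technique effect.** Assume 40 per group, a baseline gap d of 0.25 to 0.5 SD and a baseline/follow-up correlation ρ of 0.4 to 0.6. The gap carried to follow-up is dρ, so the unadjusted t-test (78 df, two-sided 5%) has noncentrality dρ / √(2/40):

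| d | ρ | noncentrality | rejection rate |
|---|---|---|---|
| 0.25 | 0.4 | 0.447 | 7.3% |
| 0.25 | 0.6 | 0.671 | 10.2% |
| 0.5 | 0.4 | 0.894 | 14.3% |
| 0.5 | 0.6 | 1.342 | 26.3% |

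Adjusting for baseline removes this component and multiplies residual variance by 1 − ρ², which is 0.84 to 0.64 (a 16% to 36% reduction).

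**Adverse device effects (ADEs), no true technique effect.** Assume a risk of 20% in incisional and 10% in primary hernia, and incisional shares of 70% and 40%. The crude rates are 0.7 × 20% + 0.3 × 10% = 17% and 0.4 × 20% + 0.6 × 10% = 14%. At 40 to 50 per group, Fisher's test rejects about 3.6% to 3.7% of the time and chi-square 6.9% to 7.5%, which is close to nominal. Under much harsher assumptions (11% versus 35% risk, incisional shares 20% versus 80%) the crude rates are 15.8% and 30.2%, and Fisher's test rejects 32% of the time at 50 per group.

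**Recurrence.** With the same rate in both groups (3.5% to 5.2%) and 40 to 50 per group, Fisher's test rejects 0.1% to 0.8% of the time and chi-square 2.6% to 4.5%. Even a 5 versus 0 split at 50 per group gives Fisher p = 0.056. A test here is nearly uninformative.

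**Multiplicity.** Recurrence has 4 time points and ADEs have 6. CCS has 3, because the pre-operative score is a baseline and not an outcome. One test each gives 13 per contrast and 13 × 3 = 39 over three contrasts. At 5% each and if independent, the chance of at least one false positive is 1 − 0.95¹³ = 48.7% for the technique contrast and 1 − 0.95³⁹ = 86.5% for all three, with 39 × 0.05 = 1.95 expected. These are upper-end figures. The incidence windows are nested, one contrast sits inside another, and the recurrence tests are very conservative.

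**The case against.** The strongest reply is that little depends on these comparisons. The primary result is a single-arm incidence with a 95% CI, no success rule or power statement uses a subgroup p-value, and Protocol 14.3 leaves subgroup analyses to study needs. That stands and limits the consequence.

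A reader might infer that SAP 7.5 gives a false reason for omitting multiplicity control. It does not. Its wording covers the primary and secondary endpoints, whose single-arm estimates are descriptive, and 7.2 treats subgroup comparisons as additional to them. The gap is that 7.5 is silent on the subgroup tests.

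A reader might also infer that every endpoint will be tested by technique. SAP 7.9 sets no limit, but the time-to-event endpoints have Kaplan-Meier estimates only, with no group test named.

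Nor do the documents show that the groups will differ, or that technique varies by site. They give no case mix, so imbalance is a plausible risk and not a finding.

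Finally, CCS is to be analysed under its User Guide, which SAP section 10 lists by title only. Whether that guide uses the baseline score cannot be settled from the text available. What can be said is that the body of the SAP names no baseline adjustment for the comparison.

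**Conclusion.** The point holds in a limited form. The SAP commits to a non-randomised technique contrast, names only unadjusted tests, acknowledges factors that could confound it, and does not state how the p-values should be read. The primary recurrence estimate is not affected.

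The clearest gain is for CCS, where a baseline measure exists. The 7% to 26% error range depends entirely on the assumed imbalance, correlation and group size. For ADEs the distortion is small under moderate assumptions and large only under extreme ones. For recurrence, with about 4 to 5 events, the tests will mostly be uninformative. The 86.5% familywise figure should not be quoted as a realistic error rate.

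**What to change.** **CCS.** For robotic versus laparoscopic repair, replace the t-test or Wilcoxon on post-operative pain and movement scores (1, 12 and 24 months) by ANCOVA. Use the corresponding pre-operative score and hernia type as covariates, applied to scores produced under the User Guide. Use a rank-based version if residuals are badly skewed. For the two hernia-type contrasts, adjust for the pre-operative score only, since hernia type is the exposure there. The pre-operative form in Protocol Appendix B has no mesh-sensation item, so that item has no baseline covariate.

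**ADEs.** Report the risk difference with 95% CI, stratified by hernia type for the technique contrast where counts allow.

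**Recurrence.** Report rates and CIs by group without a test.

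**Presentation.** Tabulate baseline characteristics, hernia type and site by technique. Add to SAP 7.5 that all three subgroup comparisons are exploratory and that no claim rests on a p-value.

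**Cost.** SAP wording and standard procedures on data already collected. A few subjects with missing pre-operative CCS would drop out of the adjusted analysis. Residual confounding by defect size, BMI and site would remain and should be acknowledged in the report.
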